Patients randomized to the fluoxetine treatment group will be initially prescribed fluoxetine 20mg/day. The drug will be supplied to patients in 90-day supply. For patients in the drug/placebo cohort, if severe depression (as defined by a HAM-D score of >24 or a PHQ-9 score >20 or positive endorsement on the PHQ-9 suicide items 2 or 3) is persistent at any study time points, an additional fluoxetine dose of 20mg/day will be administered for 40mg total dose for fluoxetine group.

If severe depression is persistent at any study time points for patients randomized to the placebo group (as defined above), they will be prescribed 20 mg of fluoxetine.

The research assistant will administer an approximately 45-minute interview at up to five time points to all patient-subjects: upon enrollment (prior to hospital discharge) as a baseline assessment, and up to four follow-up visits within 18 months after discharge from the hospital.

The goal will be to do these assessments at the six-week, six-month, and one-year follow-up appointments, taking into consideration that the actual appointments frequently do not occur exactly on the intended timescale. The trial period will be for 12 months after discharge; however, should we need to speak with patients or if they miss their 12 month appointment, we will allow for another timepoint within 18 months.

The interview questionnaires will assess depression and health-related quality of life, medication compliance, drug side effects and pregnancy, either in person, over the phone, via email, or mail. If the participant endorses serious side effects, the event will immediately be reported to and reviewed by the study PI for its relatedness to the study and it will be reported to IRB in accordance with University of Washington IRB reportable event guidelines.

Depression will be assessed using the Hamilton Rating Scale for Depression (HAM-D) and the Patient Health Questionnaire (PHQ-9). Health-related quality of life will be assessed using the Medical Outcomes Short Form Health Survey (SF-36). All measures will be assessed at each time point.

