For patients reaching the end of the study and choosing to discontinue the study drug, the two week weaning period will begin at the completion of the 12-month trial period. Patient education regarding continuation or discontinuation of SSRI treatment at the completion of the study will be provided 90 days prior to reaching the end of the study, regardless of treatment group. From time to time, members of the study team may contact the patient to ensure medication compliance and answer questions about medications and the study the subject may have.

If any patient, in the drug vs. placebo demonstrates severe depression (as defined by a HAM-D score of >24 or a PHQ-9 score >20 or positive endorsement on the PHQ-9 suicide items 2 or 3) is persistent at any study time points, patient will be immediately directed to their physician for further evaluation. If a patient endorses suicidal ideation, they will be immediately referred to the psychiatric service for further urgent mental health evaluation before a dosage increase is considered. If a patient is removed from the study, that data will be included in the subsequent data analysis.

After a final timepoint at approximately 1 year after hospitalization (but up to 18 months), the subjects' study enrollment will be complete.

Criteria for discontinuing or modifying allocated interventions

Patients may be withdrawn from the research without their consent if the patient is no longer able to participate in the research protocol. In any case that a patient-subject will be discontinuing the drug, we will taper over two weeks, halving the dose each week.

Outcome Measures

- For all subjects enrolled in the study, relevant clinical and demographic data, including PHI such as name, date of birth, dates related to hospital stay, medications, and medical record number.
- Montreal Cognitive Assessment (MoCA)- 30-item questionnaire to determine cognitive status.
- Patient Health Questionnaire 9 (PHQ9): 9-item questionnaire to treat and diagnosis depression.
- Hamilton Rating Scale for Depression (HAM-D: 30-item questionnaire to treat and diagnosis depression. This will be given if a patient exhibits depression based on the PHQ9 score.
- The Short Form (36) Health Survey (SF-36): 36-item questionnaire to assess health-related quality-of-life.
- Barthel Index: Scale used to determine functional status, measuring performance in activities of daily living.

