Based upon previous studies we anticipate the rate of depression in the treatment group to be 7.3% and the rate of depression in the placebo group to be 21.2%, as determined by the HAM-D score. It is estimated that 200 patients are eligible per year, however we have conservatively estimated enrolling 20 patients to account for recruitment and retention rates. Power calculations show a large-scale trial would require 224 total patients. We anticipate analysis at 1-year (as funded from this proposal) will demonstrate the feasibility of both the randomized administration of antidepressant medication to the post-SAH population, as well as prospectively define the rate of new depression and the effect of SAH on health-related quality of life.

Recruitment

Patients will be recruited and screened for participation by a member of the research team prior to discharge. Patient inclusion and exclusion will be determined by the medical record as well as in-person by the provider. The Montreal Cognitive Assessment will be administered prior to the consent to determine baseline cognitive state. We will also conduct screening to determine if the patient is currently receiving therapy for depression or related mental health diagnoses. Any recruiter who administers the MoCA completes MoCA training and certification. Patients scoring >20 on the MoCA are considered of appropriate cognitive function to participate in the study.

Patients recruited for the drug vs placebo cohort will be provided with a detailed explanation regarding the study protocol, occurrence of depression in aneurysmal subarachnoid hemorrhage and the potential treatment effects of fluoxetine. Patients will have an opportunity for questions before providing before consent. Decisional capacity will be determined by having participants confirm their understanding of the study purpose and procedure, and the risks, benefits and alternatives to participating in the study.

Relevant clinical and demographic data such as name, date of birth, dates related to hospital stay, medical record number, area of the ruptured aneurysm, Glasgow Coma Score, Fisher Grade, Hunt and Hess Grade, Medications, medical history, and comorbidity which will be maintained in a secure screening and recruitment log. Patients can choose to provide consent anytime between approach and discharge. Patients may revoke their informed consent at any time by contacting the research team.

Assignment of interventions: allocation

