Sequence generation

Simple randomization schemes will be utilized for the drug cohort and placebo cohort. For each cohort, subjects will be randomized in a 1 to 1 ratio to receive either the SSRI antidepressant or placebo drugs. Randomization will be done after the participant or

LAR as signed the ICF. Randomization will be performed by the study pharmacist. Study team, study assessor, study investigator is blinded until the subject exits the study, need to unblind for medical intervention, or end of the study.

Assignment of interventions: Blinding

Who will be blinded

Trial participants, care providers, outcome assessors will stay blinded. Placebo vs study drug will be prepared and dispensed by local study pharmacist. Only the study pharmacy will know the designation of each participant until the clinical team request the information for health care purposes or when the participants exit the study.

Procedure for unblinding if needed

If an adverse event occurs in which the disclosure of the treatment arm is necessary for medical treatment, the disclosure will be provided to the patient and/or provider.

Data collection and management

Plans for assessment and collection of outcomes

Preventative treatment of poststroke depression in aneurysmal subarachnoid hemorrhage					
Activity	Initial Screening	Baseline	6-week	6-month	12-month
Eligibility Screen	x				
Montreal Cognitive Assessment (MoCA)*	x				
Enrollment	x				
Consent	x				
OnCore/EPIC Update	x	x	x	x	x
Pharmacy Prescription Fluoxetine (every 90 days)		x	x	x	
Patient Health Questionnaire (PHQ-9)		x	x	x	x

Hamilton Rating Scale for Depression (HAM-D)**		x	x	x	x
36-Item Short Form Survey (SF-36)		x	x	x	x
Barthel Index		x	x	x	x
Hamilton Anxiety Rating Scale (HAM-A)		x	x	x	x
Multidimensional Scale of Perceived Social Support		x	x	x	x
Sleep Disturbance (PROMIS)		x	x	x	x
Self Report Health Service Utilization and Medication Use		x	x	x	x
Fatigue Severity Scale (FSS)		x	x	x	x
Disclosure of Interventional Cohort					x
*MoCA score must score more than 20 in order to be enrolled and consented into the study					
**HAM-D only conducted when pt scores greater than 4 on PHQ-9					

Confidentiality and Data management

All research data will be deidentified. A single-master key will be retained. All data will be stored on a secure research database or in a secure cabinet on a secure floor.

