Access to identifiers will be limited to the study team. Data will be classified as Level 4 risk. U1-U13, D1-D9 will apply to all data. S1-S20 will be utilized; local procedures will be utilized in addition to the protections afforded by utilizing the UW OneDrive. P1-P3 will be utilized for non-digital records. T1-T8 will be utilized for data transmission. We do not intend to utilize vendors, but if vendors are utilized we will adhere to V1.

Statistical methods

Statistical methods for primary and secondary outcomes

In addition to patient-level measures, relevant clinical and demographic data will be

obtained for the descriptive statistics of the cohort. For each time point we will determine the rate and severity of the outcome measures. We will utilize linear mixed models to determine to determine the treatment effect of preventative fluoxetine administration in patients surviving subarachnoid hemorrhage. Important confounders will be determined and adjusted for in the analysis. The primary outcome will be analyzed at the one-year time point. The intermediate time points will be obtained to determine the longitudinal progression of the mental health status and functional ability in this patient population.

Oversight and monitoring

Composition of the coordinating centre and trial steering committee

The PI (or approved co-investigator) will monitor the study with prompt reporting of adverse events and other study related information to the IRB and other agencies as appropriate. Non-serious adverse events and unrelated serious adverse events will be reported in the annual progress report. Serious adverse events that could be related to the study should be reported within 7 days of becoming aware of the event. At any time, if a patient presents suicidal ideations, the patient will be immediately referred to psychiatric service for further evaluation and the event reported. Team meetings by the PI and staff will be conducted on a routine basis to discuss any new adverse events or changes in the protocol. This plan will be revised and updated if the benefit-risk analysis changes.

Composition of the data monitoring committee, its role and reporting structure

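### HAM-D is scheduled for everyone in one section but only after a positive PHQ-9 in two others, so HAM-D severity on observed scores would compare subsets selected after randomisation

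*Combined protocol and SAP*

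**What the plan says.** The combined protocol and SAP gives three rules for one scale.

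- **Intervention description:** after naming HAM-D, PHQ-9 and SF-36, it says "All measures will be assessed at each time point".
- **Outcome Measures, HAM-D entry:** "This will be given if a patient exhibits depression based on the PHQ9 score". No cut-off is given.
- **Plans for assessment and collection of outcomes, schedule table:** HAM-D is marked at baseline, 6 weeks, 6 months and 12 months, with the footnote "HAM-D only conducted when pt scores greater than 4 on PHQ-9". The footnote does not say which visit's PHQ-9 counts; I read it as that visit's. PHQ-9 itself carries no condition.

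The analysis text is in Statistical methods for primary and secondary outcomes: "For each time point we will determine the rate and severity of the outcome measures", and "We will utilize linear mixed models to determine to determine the treatment effect of preventative fluoxetine administration". It names no scale, does not identify the primary outcome beyond placing it at one year, and does not say what happens when HAM-D was not given. The Sample size section ties depression to HAM-D: 7.3% on fluoxetine, and "the rate of depression in the placebo group to be 21.2%, as determined by the HAM-D score".

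There is a related inconsistency. Outcome Measures describes the Fatigue Severity Scale as measuring fatigue in patients who show depression, while the schedule table lists it at every visit without a condition.

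**The concern.** A follow-up PHQ-9 is a post-randomisation measurement that fluoxetine is expected to change. If HAM-D exists only where PHQ-9 exceeds 4, the fluoxetine patients with a HAM-D are those who scored above the cut-off despite treatment, and the placebo patients with one are those who scored above it without treatment. Randomisation does not make these two groups alike. A difference in mean HAM-D between them mixes the treatment effect with the effect of selection.

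The background text expects fluoxetine to improve both the incidence and the severity of depression, so a HAM-D severity comparison is a natural output of the plan. At stake is whether that output could be read as a treatment effect. At baseline the same footnote leaves HAM-D missing for low scorers, but treatment cannot have caused that.

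**Working it through.** **Plan's own figure.** The point turns on no figure in the plan. For completeness, 224 is approximately reproduced from 21.2% versus 7.3%: two-sided 5%, 80% power with continuity correction gives 113 per arm, 226 in total. It is unaffected here.

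**Inputs from the documents.** HAM-D depression rates of 21.2% and 7.3%; 1:1 allocation; the plan "conservatively estimated enrolling 20 patients". I take 10 per arm, assuming that all 20 are randomised, which the Sample size section does not say.

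**Assumptions not in the documents.** 40–70% of placebo patients pass the PHQ-9 screen; the scales correlate (ρ) at 0.6–0.9; the PHQ-9 effect is a fraction k = 0.5–1.0 of the HAM-D effect in SD units. The only HAM-D threshold in the documents is for severe depression ("as defined by a HAM-D score of >24 or a PHQ-9 score >20"), so the model works from the rates and not from a score.

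**Normal scores, additive effect.**

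1. HAM-D shift: z(0.788) = 0.800 and z(0.927) = 1.454, so δ = 0.654 SD.
2. Let g be the screen on the standardised placebo PHQ-9 scale and λ(x) = φ(x)/(1 − Φ(x)). Observed-only difference = δ − ρ[λ(g + kδ) − λ(g)].
3. Example with 50% of placebo passing, ρ = 0.7, k = 1: g = 0, λ(0) = 0.798, λ(0.654) = 1.256. Observed difference = 0.654 − 0.7 × 0.458 = 0.334 SD, or 51% of the true effect. Only 25.6% of fluoxetine patients pass.
4. Over 48 combinations: 33–83% of the true effect, median 64%. The bias is (1 − 0.835) × 0.654 = 0.11 SD to (1 − 0.332) × 0.654 = 0.44 SD.

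**Other score shapes (simulation).** Right-skewed (gamma) scores with a proportional effect give 80–153% of the true difference. A model in which treatment changes only the share of cases, with 80–100% of cases passing, gives 62–203%. Over all three models the range is 33–203%.

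**Mixed model.** A four-visit random-intercept model on screened HAM-D gave a 12-month effect of 0.51–0.78 of the true one with normal scores (3 scenarios) and 0.83–1.31 with gamma scores (7 scenarios). It does not remove the selection, because it ignores the PHQ-9 that caused the missing scores.

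**Depression rate.**

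- Patients at or below the cut-off counted as not depressed and kept: in the example above, 18.9% versus 5.9%, a difference of 12.9 points before rounding. Over the grid it is 10.4–13.9 points (median 13.2; 10.1–13.9 if skewed), against 21.2 − 7.3 = 13.9.
- The same patients dropped from the denominator: placebo 29–51%, fluoxetine 12–38%.

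**Sampling error at 10 per arm.**

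- Severity, everyone measured: √(2/10) = 0.45 SD.
- Severity, screened scores: 0.46–0.81 SD (simulated, normal scores, 8 scenarios).
- Risk difference: √(0.212 × 0.788/10 + 0.073 × 0.927/10) = 15.3 points.
- Patients with a 12-month HAM-D (normal model): 4–7 of 10 on placebo and 2–6 of 10 on fluoxetine, 6–13 of 20 in total. The chance of fewer than three on fluoxetine is 2–73%.

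None of these models represents the treatment change for severely depressed patients, which would alter the upper tail of scores.

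**The case against.** The strongest reply is that the harm depends on an analysis the plan does not state. No scale is named for the mixed model, and PHQ-9 is collected from everyone and gives an unselected severity measure. The footnote can be read as an ordinary two-stage assessment, with the Intervention description speaking only generally. On the one HAM-D quantity the documents quantify, the depression rate, little is lost. All of this stands, and it limits the point to HAM-D severity on observed scores. It does not remove it: the plan asks for severity at each time point, HAM-D is one of its two depression scales, and nothing steers the analyst away from observed scores.

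A second reply is that the missing scores depend on a recorded PHQ-9, so a model using both scales could recover the effect. With normal scores, regression on PHQ-9 within arm recovered 97–100% in four scenarios. But the plan specifies no such model, and with no HAM-D at PHQ-9 of 4 or less it would rest on extrapolation.

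A reader might also infer more than the documents support:

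- *That the HAM-D effect would be understated.* That holds in the normal model only; other shapes reverse it.
- *That the depression rate is badly inflated.* That needs low scorers to be dropped from the denominator, which the plan neither states nor rules out. The Outcome Measures wording leans towards counting them as not depressed.
- *That the primary endpoint is compromised.* The plan does not identify HAM-D severity as primary.
- *That a 224-patient trial would be misled.* That trial is mentioned, not planned here. With screened scores its SE would be 0.125–0.228 SD at 112 per arm, and the normal-model bias exceeds 1.96 SE in only 12 of 48 combinations.

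**Conclusion.** The point holds in limited form and should be fixed. The schedule contradicts itself. If the footnote is followed, any HAM-D severity summary or mixed model on observed follow-up scores compares subsets selected after randomisation, with no rule in the plan for the rest.

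The direction and size of the bias cannot be determined from the documents. The range of about one third to about twice the true difference rests on assumed score distributions and shows only that the error could be material in either direction. In this study of about 20 patients, sampling error is at least as large as the bias in the normal-score model, so the gain is an interpretable analysis more than a different answer. The HAM-D rate is little affected under the natural counting rule, and PHQ-9 results are unaffected. The Fatigue Severity Scale would face the same selection if its description is meant as a condition. Confidence is high on the contradiction and the mechanism, and low on any single magnitude.

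**What to change.** Reconcile the Intervention description, the HAM-D entry in Outcome Measures and the schedule footnote.

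**Preferred.** For outcome assessment, remove the PHQ-9 condition, so that every randomised patient has HAM-D at each scheduled visit, by interview in person or by phone. A HAM-D not done is missing, not a negative result. Cost: a few more interview minutes for low scorers, and no email or mail for this scale, although the Intervention description allows both modes. Observer-rated items such as psychomotor slowing need an interviewer and are harder to rate by phone.

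**If the screen stays.** Use one cut-off in both places, applied to that visit's PHQ-9, and add to the statistical methods:

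> For the depression rate, patients at or below the PHQ-9 cut-off count as not depressed and stay in the denominator; patients above the cut-off without a HAM-D are missing. PHQ-9 total is the depression-severity outcome in the mixed model. HAM-D scores above the cut-off are described by arm and not tested as a treatment effect.

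Cost: HAM-D severity is not tested, and some HAM-D cases below the cut-off are missed. Under the normal-model assumptions this is 6–25% of placebo cases at a correlation of 0.6, and 4% or fewer at 0.9.

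**In either case,** state whether the Fatigue Severity Scale is given to everyone or only to patients showing depression.

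These changes concern outcome collection and analysis only. How HAM-D feeds the treatment-change rule in the Intervention description is for the sponsor to reconcile, and nothing is proposed there.

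### The target effect is a HAM-D depression rate, but the only treatment-effect model is a linear mixed model with no named outcome, and HAM-D may be collected only from patients with PHQ-9 above 4

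*Combined protocol and SAP*

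**What the plan says.** **Target effect.** The Sample size section takes 7.3% for the fluoxetine arm from earlier research. Its placebo assumption is "the rate of depression in the placebo group to be 21.2%, as determined by the HAM-D score". It adds that "Power calculations show a large-scale trial would require 224 total patients". For the present study it says "we have conservatively estimated enrolling 20 patients to account for recruitment and retention rates", and that the one-year analysis "will demonstrate the feasibility of both the randomized administration of antidepressant medication to the post-SAH population". Describing new depression and quality of life are the other stated aims.

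**Analysis.** Statistical methods for primary and secondary outcomes says that both rate and severity will be determined at each visit, then: "We will utilize linear mixed models to determine to determine the treatment effect of preventative fluoxetine administration". No dependent variable is given. "The primary outcome will be analyzed at the one-year time point", but that outcome is not identified. No method for binary data appears anywhere.

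**Collection of HAM-D.** The footnote to the schedule table reads "HAM-D only conducted when pt scores greater than 4 on PHQ-9". The Outcome Measures list likewise makes HAM-D conditional on the PHQ-9 result. The Intervention description, by contrast, has all measures taken at each time point.

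**Cut-off.** The only HAM-D threshold in the document is above 24. It marks severe depression for patient management and is not offered as the definition behind 7.3% and 21.2%.

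**The concern.** The effect of interest is a difference between two proportions, while the named model is built for a continuous outcome. The reader must guess what it is fitted to, and both natural guesses lead to trouble.

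- **HAM-D score.** Under the gate, the score is absent by design at every visit where PHQ-9 is 4 or less. PHQ-9 at follow-up is measured after randomisation, and treatment is meant to lower it. The patients with a HAM-D are then not comparable between arms.
- **Depression yes/no.** With very few events, a linear model gives impossible limits for a rate, and its p-value depends on a choice the plan does not make.

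At stake is whether the one-year analysis can describe the rate of new depression and give a usable effect estimate for the larger trial. Bias from the gate does not shrink with sample size, so it would carry into that trial if the design were copied.

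**Working it through.** **1. The plan's own figure.** Inputs from Sample size: p1 = 0.073, p2 = 0.212, difference 0.139, mean 0.1425. Alpha and power are not stated, so I assume two-sided 5%.

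n per arm = [1.96 √(2 × 0.1425 × 0.8575) + z_β √(0.073 × 0.927 + 0.212 × 0.788)]² / 0.139².

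- 85% power, no continuity correction: 112.0.
- 80% power, continuity-corrected: 98.1 becomes 112.0.

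Either gives 224 to the nearest integer (226 if each arm is rounded up). So 224 does rest on a comparison of two proportions.

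**2. If the model is fitted to gated HAM-D scores.** The documents give no score distributions. Assumptions: HAM-D and PHQ-9 bivariate normal with correlation ρ = 0.6 to 0.8, PHQ-9 SD 5, placebo PHQ-9 mean 4 to 8, true benefit 0.4 SD on both scales (2 PHQ-9 points), one visit, observed cases only.

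In SD units, the mean HAM-D among patients with PHQ-9 above 4 is shifted by ρλ(a), where a = (4 − mean)/5 and λ(a) = φ(a)/(1 − Φ(a)). The difference seen is 0.4 − ρ[λ(a_F) − λ(a_P)], so the share lost is ρ[λ(a_F) − λ(a_P)]/0.4.

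| Placebo mean | λ(a_P) | λ(a_F) | Lost, ρ = 0.6 | Lost, ρ = 0.8 |
|---|---|---|---|---|
| 4 | 0.798 | 1.069 | 41% | 54% |
| 6 | 0.562 | 0.798 | 35% | 47% |
| 8 | 0.368 | 0.562 | 29% | 39% |

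Placing the gate at 4.5, because PHQ-9 is an integer score, gives 31% to 56%. Roughly 30-55% of the effect is lost.

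**3. If the model is fitted to depression yes/no.** Assume all 20 are randomised, 10 per arm, and complete.

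- Expected events: 10 × 0.073 = 0.73 and 10 × 0.212 = 2.12. Chance of none on fluoxetine: 0.927¹⁰ = 0.47.
- 0/10 v 2/10: residual variance 1.6/18 = 0.0889; SE of one arm's rate √(0.0889/10) = 0.094. The 95% interval for the fluoxetine rate is 0 ± 19.8% (t, 18 df) or 0 ± 18.5% (z).
- Over all possible results at the planned rates, the lower limit for the fluoxetine rate is below zero in 93% (t) or 92% (z) of trials.
- 0/10 v 3/10: residual variance 2.1/18 = 0.1167; SE of the difference √(0.1167 × 2/10) = 0.1528; statistic 0.3/0.1528 = 1.964. p = 0.0495 with z, 0.065 with t on 18 df. Fisher's exact test gives 0.21.

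**4. Type I error at 10 per arm** (exact enumeration, single visit, nominal 5%), at common rates of 7.3%, 14.25% and 21.2%:

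- linear model, t: 0.4%, 1.9%, 3.1%
- linear model, z: 3.0%, 7.5%, 8.8%
- Fisher: 0.04%, 0.3%, 0.8%

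A simulated random-intercept linear mixed model on binary data at three visits (600 trials per rate, assumed logit random-intercept SD 2) gave about 2% to 6% under either reference. Some fits raised convergence warnings, so this is a rough check.

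**The case against.** **The plan may mean the model for severity scores.** That is a fair reading: the sentence before it mentions both rate and severity, and a linear mixed model suits PHQ-9 or SF-36. It disposes of the yes/no reading for those scales, but leaves the rate, the only effect the document quantifies, with no comparison method.

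**A mixed model drops visits, not patients.** This stands: anyone with PHQ-9 above 4 at some visit still contributes, and the single-visit percentages are not estimates for the longitudinal model. The bias is not removed, however. Missingness is decided by the same-visit PHQ-9, which a model of HAM-D alone does not contain.

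**The gate may not apply.** If every measure really is taken at every visit, the selection problem disappears. Two places in the document support the gate and one contradicts it.

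**Stronger readings the documents do not support.** A reader might infer that this trial was sized on the depression rate. It was not: 224 belongs to a hypothetical large-scale trial, and 20 is a recruitment and retention estimate for a feasibility stage. A reader might also infer that the linear model inflates type I error. The plan names neither the binary outcome for that model nor a reference distribution. Inflation, to at most 8.8%, appears only with z at a single visit; with t the rate stays below 5%. Nor does the gap to Fisher's p-value prove the linear model wrong, because Fisher is itself far below nominal here. Sparse events in 20 patients are the main cause.

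**Conclusion.** A specification gap with a real consequence. The outcome, cut-off, scale, model and handling of patients without a HAM-D are not tied together. The most serious consequence arises if HAM-D scores are modelled under the gate: the comparison is conditioned on a variable that treatment is meant to change, and the effect is pulled toward zero. The loss of roughly 30-55% is illustrative. It rests on the assumed score distributions and a single visit, and no document figure can confirm it. On the yes/no reading, the defects are impossible interval limits and a verdict that can hinge on an unstated choice, assuming 10 complete patients per arm. The finding is worth acting on before analysis. It does not show that the trial is wrongly sized or its error rate inflated.

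**What to change.** 1. Reconcile the Intervention description with the Outcome Measures list and the schedule footnote on when HAM-D is given.
2. Name the primary outcome: HAM-D-defined depression at one year, with a prespecified cut-off. The sponsor should confirm which definition lies behind 7.3% and 21.2%; the document does not give it.
3. If the gate stays, count patients with PHQ-9 of 4 or less as not depressed for the analysis, so that every assessed randomised patient enters. State this as an assumption, since the gate leaves it uncheckable within the trial.
4. Report the risk difference with a score or exact interval, as estimation and not as a test of efficacy.
5. Keep linear mixed models for named scales taken on everyone (PHQ-9, SF-36), with baseline as covariate and a small-sample degrees-of-freedom correction.

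The cost is a few lines of SAP wording and wider intervals. For 0/10 v 2/10, the linear-model t interval for the difference is 0.20 ± 2.101 × 0.1333, or −8% to 48%. The score-based (Newcombe) interval uses Wilson limits of 0 to 0.278 and 0.057 to 0.510. It runs from 0.20 − √(0.143² + 0.278²) = −11% to 0.20 + 0.310 = 51%. That is 62 points wide against 56, and reflects what 20 patients can show.
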